#### **Post Nasal Allergen Challenge Telephone Follow up (24 hours after Visit 2)**

Subjects will be contacted for phone call follow-up 24 hours after allergen challenge (see phone script below)

#### **Discontinuation visit: (5-10 days after challenge)**

1. Vital signs
2. PE (including oral exam)
3. Spirometry

#### **Endpoints**

The primary endpoint for this study is  $\Delta$ eosinophils/mL of nasal lavage fluid (post-allergen challenge minus pre-allergen challenge values), comparing e-cigarette users to cigarette smokers and non-smokers. A secondary endpoint will be  $\Delta$ Eosinophilic cationic protein ( $\Delta$ ECP), a marker of eosinophil activation. Exploratory endpoints as well as safety criteria for stopping involvement of an individual in the protocol or suspending the overall study are outlined below.

## **Exploratory Endpoints**

Exploratory endpoints of interest from examination of *epithelial lining fluid (ELF)* and *nasal lavage fluid* collection include:

1. Cytokines and chemokines: Leukotriene C4, D4, and E4, PGD2, GM-CSF, IL-4, IL-8 IL-13, RANTES, Eotaxin, soluble CD14, LPS-binding protein, Dermatophagoides Farinae (Der F) specific and total IgE, TNF, IL1, IL6, CCL2 (MCP-1), CCL3 (MIP-1 $\alpha$ ), CCL4 (MIP-1 $\beta$ ).

Exploratory endpoints of interest from examination of *nasal epithelial cell* sampling include:

2. mRNA to evaluate gene expression profiles: TLR2, TLR3, TLR4, TLR7, NLRP3, NLRP12, and CD14 expression.

Exploratory endpoints of interest from examination of *peripheral blood* include:

3. Complete blood count and differential
4. mRNA from peripheral blood mononuclear cells (PMBCs)
5. Cytokine profile examined in nasal fluid samples
6. Flow cytometry for cell surface markers: CD11b, CD14, CD80/86, HLA-DR, TLR 4, Fc $\epsilon$ R1

## **Safety measures**

Criteria for safety of a given individual following a specific challenge will include (failure of which would result in discontinuation of that subject from further study):

1. No greater than 10% decrease in FEV1 from pre-challenge values following a nasal allergen challenge to *D. farinae* allergen.
2. FEV1 must recover without treatment to within 85% of baseline within 6 hours of challenge without treatment, or if albuterol is employed the volunteer must recover to within 90% of baseline value within 20 minutes. All persons with a  $\geq 10\%$  decrease in FEV1 or those with respiratory symptoms will be given albuterol.
3. If albuterol therapy is needed more than three times within the first hour or more than 3 times during the observation period.
4. Requirement of oral corticosteroid treatment due to asthma exacerbation or other serious allergic reaction associated with challenge.
5. Evidence of upper airway obstruction, defined by the subject complaining of difficulty breathing, excessive salivation, changes in voice quality, and stridor. If an individual experiences evidence of upper airway obstruction, the subject will be treated with epinephrine via administration of an EpiPen device, as well as topical application of epinephrine if there is uvular involvement.

Criteria for safety within the entire protocol (failure of which would result in suspension of further study until consultation with the CBER of the FDA and the UNC IRB) will include the following:

1. No more than 20 % of patients will fail the individual safety criteria outlined above. As it is anticipated that 45 subjects will be recruited into this study, then 9 or more subjects who fail individual safety measures will result in suspension of further study until consultation with the CBER of the FDA.
2. No occurrence of any Serious Adverse Event

Subjects will be under direct supervision for at least 90 minutes post challenge and will have contact information for after-hours access to a study physician. In the event of an unexpected event, such as wheezing, urticaria or other allergic symptoms, the physician will follow the usual medical standard of care to treat the subject.

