##### **Visit 0: Screening allergen challenge day studies:**

1. Consent obtained
2. Urine pregnancy test for females of child bearing potential

3. Vital signs
4. Medical history (including medications) and physical exam (including oral exam, noting the uvula), and a smoking use questionnaire will be obtained.
5. Skin testing for *D farinae* sensitization (unless previously obtained).
6. Baseline spirometry
7. Lavage with normal saline to both nares to clear secretions and prepare for placement of allergen.
8. Total nasal symptom score (TNSS)
9. Peak nasal inspiratory flow (PNIF) measurement
10. Graded nasal allergen challenge using both nares with TNSS after each dose.  
Nasal allergen challenge will be provided in a graded dose fashion 0 AU, 100 AU, 500 AU and then 1,000 AU separated by 10 minutes. Dilutions will be provided by the University of North Carolina Hospitals Investigational Drug Service. Over 10 minutes, symptoms will be monitored and scored. Increasing concentrations of dust mite allergen dilution are deposited into the nose until the TNSS reaches a total of 8 or more (described below) and PNIF is reduced by at least 50%. An oral exam will occur prior to each dose. The cumulative allergen dose producing a TNSS of  $\geq 8$  and reduction in PNIF of  $\geq 50\%$  will be considered the provocative dose of allergen. Failure to achieve TNSS of  $\geq 8$  and reduction in PNIF of  $\geq 50\%$  will result in screen failure.
11. Subjects will be monitored for 90 minutes from the last dose of nasal allergen. Oral and upper airway exam, vital signs and spirometry will be performed at 30 and 60, and a physical exam at 90 minutes. At 90 minutes, if no significant findings on exam and no significant reduction in FEV1 (<10% reduction from baseline), the subject will be discharged.

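### Read literally, the airway-obstruction criterion needs all four signs together, and no stated rule in section 6.1 requires dosing to stop for new uvular swelling or a non-serious systemic reaction

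*Combined protocol and SAP*

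**What the plan says.** All references are to section 6.1 of the combined protocol and SAP.

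- **Individual criteria (6.1.e, Safety measures).** The lead-in reads "Criteria for safety of a given individual following a specific challenge will include", and failing a criterion discontinues the subject. Criteria 1 to 4 concern an FEV1 fall above 10%, FEV1 recovery, repeated albuterol, and oral corticosteroids for an asthma exacerbation or serious allergic reaction. Criterion 5 concerns upper airway obstruction, "defined by the subject complaining of difficulty breathing, excessive salivation, changes in voice quality, and stridor". Its treatment is an EpiPen, "as well as topical application of epinephrine if there is uvular involvement".
- **Other reactions (same section).** Criterion 2 adds that "those with respiratory symptoms will be given albuterol". The closing paragraph says that for an unexpected event "such as wheezing, urticaria or other allergic symptoms, the physician will follow the usual medical standard of care". Any serious adverse event suspends the whole study.
- **Escalation (Visit 0, item 10).** "Increasing concentrations of dust mite allergen dilution are deposited into the nose until the TNSS reaches a total of 8 or more" and PNIF has fallen by at least 50%. The nasal allergen challenge procedure repeats this and adds the maximal dose as an end point. A subject who does not reach both thresholds is a screen failure.
- **Examinations (Visit 0, items 10 and 11).** "An oral exam will occur prior to each dose". After the last dose, "Oral and upper airway exam, vital signs and spirometry will be performed at 30 and 60" minutes, with a physical exam at 90 minutes that decides discharge.
- **Re-challenge (Visit 2, item 10).** The dose is the provocative dose from Visit 0, which Visit 0 defines as a cumulative dose.
- **Discretion (6.1.f).** A physician may withdraw a subject at any point in the subject's interest.

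**The concern.** The protocol reports an allergic uvulitis after an earlier nasal challenge and schedules oral exams to look for a recurrence. Yet no rule for stopping a dose or discontinuing a subject uses the finding. Criterion 5 mentions the uvula only to choose an added treatment once obstruction is already present, and its list of signs is joined by *and*. Stridor with a voice change but no excess salivation would not meet the definition as written.

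Generalized urticaria treated with an antihistamine is in a similar position. Section 6.1.f names urticaria, flushing, hypotension and anaphylaxis as hypothetical risks, but the stated response to urticaria is treatment, with nothing said about further dosing.

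What is at stake is the safety of an individual who reacts during or shortly after the Visit 0 challenge. The primary endpoint and its analysis are not affected.

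**Working it through.** The check is mainly a reading of every stopping, discontinuation, exclusion and discharge statement in section 6.1, with a little arithmetic on doses and intervals.

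**Figures reproduced.**
- Dose steps are 100, 500 and 1,000 AU. Cumulative doses are 100, 100 + 500 = 600, and 600 + 1,000 = 1,600 AU, which matches the maximum in the Dosage section.
- The suspension count is 0.20 × 45 = 9, which matches the stated figure.
- The shortest interval from Visit 0 to Visit 2 is 7 + 14 = 21 days (Visit 1 and Visit 2 headings).

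**Case A: new uvular swelling at the oral exam before the 500 AU dose, TNSS 7.**
1. The escalation end point is not met, because TNSS is below 8, and the maximal dose has not been given.
2. Criteria 1 and 2 rest mainly on FEV1. Visit 0 schedules spirometry before the challenge and at 30 and 60 minutes after the last dose, so none is scheduled between steps. Criteria 3 and 4 need repeated albuterol or oral steroids. Criterion 5 needs its four signs.
3. As written, the next step is 500 AU, 10 minutes after the last and 500/100 = 5 times larger. A further 1,600 − 100 = 1,500 AU remains available. Had the swelling appeared after the 500 AU step, the next would be 1,000/500 = 2 times larger, with 1,600 − 600 = 1,000 AU remaining.
4. If the physician halts dosing here, the thresholds have not been reached. The subject is a screen failure and does not go to Visit 2.

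**Case B: swelling first seen at or after the dose that meets both thresholds.**
1. The subject qualifies, and the cumulative dose (100, 600 or 1,600 AU) becomes the Visit 2 dose.
2. The 90-minute exam governs discharge from Visit 0, not entry to Visit 2.
3. None of the 19 exclusion criteria names a reaction to an earlier challenge.
4. After 21 days or more, the pre-challenge uvula exam at Visit 2 may be normal.
5. What remains is discretionary withdrawal.

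**Case C: generalized urticaria at or after the qualifying dose, no FEV1 fall, antihistamine only.** None of criteria 1 to 5 is met. The event is not serious unless it meets the SAE definition. The stated response is standard-of-care treatment, and Visit 2 again depends on discretion.

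**What cannot be computed.** Section 6.1.f mentions over 70 earlier challenges and one uvulitis case, but does not say that the case is among them. No rate can be formed.

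**The case against.** There is a good case that the gap is small.

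- **The uvulitis was acted on.** Section 6.1.f attributes it to sniffing and lying down. This protocol forbids sniffing, aims delivery away from the pharynx and advises against lying recumbent for 4 hours. A reader might infer that the known hazard was ignored; the text does not support that. These measures stand as prevention, but they do not say what to do when swelling is seen.
- **Re-challenge is not wide open.** A reader might infer that nothing keeps a reacting subject from Visit 2. That goes too far. The screen-failure rule excludes anyone whose dosing is stopped before the end point. The 24-hour call asks about health concerns and medical visits, history is reviewed at Visits 1 and 2, and every adverse event is evaluated by a study physician. An earlier reaction would probably be known; what is missing is a required consequence.
- **The criteria are meant to stop people.** The Endpoints section introduces them as criteria for ending an individual's involvement, so it is implausible that staff would give the next dose after one was met. This stands: a sentence in the escalation rule is clarification on that point. It does not help where no criterion covers the reaction.
- **The conjunction may be ordinary drafting,** a list of typical signs. That is possible, and a physician is immediately available and unlikely to wait for all four. The point is limited to the literal reading.
- **A bare *any one of* would be worse.** The challenge is designed to block the nose, so trouble breathing through it is an intended response. Ordering an EpiPen and discontinuation for that would be a new hazard. This is right, and the qualifier must sit in the rule itself.

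**Conclusion.** The point holds in limited form. Section 6.1 states no rule that requires dosing to stop for new uvular or oropharyngeal swelling, or for a non-serious systemic allergic reaction without an FEV1 fall, repeated albuterol or oral steroids. For re-challenge, once early stopping is treated as screen failure, the gap is confined to reactions seen at or after the qualifying dose, where withdrawal is permitted but not required.

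Its size cannot be expressed as a probability. Counts of sign combinations or of scheduled exams would measure no risk, so none is offered. The benefit of the change is to individual subject safety only; a reader should not infer bias in the eosinophil endpoint, an effect on the analysis or any study-level effect.

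The conclusion assumes the literal wording of criterion 5. It is confined to section 6.1: the section on previous human experience (section 9) and the study worksheets were not available and may hold further handling.

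**What to change.** 1. **Criterion 5.** Define obstruction as *any one or more of stridor, change in voice quality, excessive salivation, or difficulty breathing not explained by nasal congestion or bronchospasm in the study physician's judgment*.
2. **New individual discontinuation criteria, without automatic epinephrine.** Add new uvular or oropharyngeal swelling on a scheduled oral exam; a systemic allergic reaction (generalized urticaria, hypotension with a threshold set by the study physicians, or anaphylaxis); and any use of epinephrine.
3. **Escalation.** In Visit 0 item 10 and in the nasal allergen challenge procedure, state that dosing also stops when any individual safety criterion is met.

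The cost is protocol wording, since the oral exams are already scheduled. The downside is that a few more subjects may be discontinued, and each would count toward the 9-of-45 suspension rule. The qualifier in item 1 limits needless epinephrine for a blocked nose or wheeze.

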### ***Definition of an adverse event (AE) and Serious Adverse Event (SAE):***

An adverse event for a given volunteer will be defined as failure of any of the safety criteria outlined in section “e”. Additionally, minor upper respiratory tract infections occurring within 96 hours of the exposure will be considered adverse events. Other, non-specified clinical illnesses, which occur within 96 hours of each challenge, will also be reported as an AE. Any decrease in lung function or increase in symptom score, as outlined in section “e” will be considered an adverse event. Any symptoms that induce a

volunteer to seek medical attention from any provider within 96 hours of challenge will be considered an adverse event.

Adverse events will be graded using Common Terminology Criteria for Adverse Events v3.0, (CTCAE website at <http://ctep.cancer.gov/reporting/ctcnew.html> and <http://safetyprofiler-ctep.nci.nih.gov/CTC/CTC.aspx>). Symptom scores will be graded as outlined elsewhere in this application.

The severity grades of AE's are defined as follows:

Grade 1: Mild AE

Grade 2: Moderate AE

Grade 3: Severe AE

A serious adverse event will be defined as any event that requires hospitalization or results in life threatening illness or injury, permanent (or likely to be permanent) illness or injury, or death if these events occur within 96 hours of challenge (or if the clinical scenario leading up to hospitalization, illness, injury or death begins within 96 hours of a challenge).

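### The study-suspension rule states two thresholds that disagree at exactly 9 of 45 failures, and the FEV1 recovery criterion cannot operate alongside its own albuterol clause (minor)

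*Combined protocol and SAP*

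**What the plan says.** Everything at issue stands under Safety measures in section 6.1 e.

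**Study level.** Failing either of two criteria suspends the study pending consultation. One criterion concerns serious adverse events. The other reads "No more than 20 % of patients will fail the individual safety criteria outlined above". The next sentence takes 45 as the anticipated recruitment and concludes that "9 or more subjects who fail individual safety measures will result in suspension of further study".

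**Individual level.** Failing the individual criteria discontinues the subject and feeds the study-level count. Two of the criteria concern FEV1:
- Criterion 1: "No greater than 10% decrease in FEV1 from pre-challenge values following a nasal allergen challenge".
- Criterion 2, untreated route: "FEV1 must recover without treatment to within 85% of baseline within 6 hours of challenge without treatment".
- Criterion 2, treated route: "if albuterol is employed the volunteer must recover to within 90% of baseline value within 20 minutes".
- Criterion 2, closing sentence: all persons with a 10% or larger "decrease in FEV1 or those with respiratory symptoms will be given albuterol".

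The adverse event section uses the same list: "An adverse event for a given volunteer will be defined as failure of any of the safety criteria outlined in section" e.

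**The concern.** Apart from the serious adverse event trigger, this is the only rule that suspends the whole study. The count is presented as following from the percentage, yet the two give opposite answers at the ninth failure. The section on reporting of AEs and SAEs requires the FDA and the IRB to be told within 24 hours once suspension criteria are met, so a reporting duty also turns on that subject.

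The FEV1 criteria decide who enters the count. A criterion that describes recovery suggests that recovery matters to the outcome. If criterion 1 has already failed everyone who needs to recover, either the recovery tests have no function, or the authors meant recovery to count for something that the text does not state.

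**Working it through.** **1. The plan's own figure.** Inputs: 20% and 45, both from Safety measures. 0.20 × 45 = 9.0, so the stated 9 reproduces as the product. The disagreement lies in the inequality.

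| Failures of 45 | Percent | Percentage sentence | Count sentence |
|---|---|---|---|
| 8 | 17.8 | continue | continue |
| 9 | 20.0 | continue | suspend |
| 10 | 22.2 | suspend | suspend |

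At every other count from 0 to 45 the two sentences agree.

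**2. How often this could matter.** The documents give no failure rate; section 6.1 f says the earlier studies did not regularly measure lung function after challenge. The rates below are therefore assumptions. X is the number of failures, binomial with n = 45, with independent subjects all followed to the end.

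| Assumed rate | P(X ≥ 9) | P(X ≥ 10) | P(X = 9) |
|---|---|---|---|
| 5% | 0.0003 | 0.0001 | 0.0003 |
| 10% | 0.0320 | 0.0120 | 0.0200 |
| 15% | 0.2255 | 0.1274 | 0.0980 |
| 20% | 0.5593 | 0.4120 | 0.1472 |
| 25% | 0.8275 | 0.7200 | 0.1074 |

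Each entry is rounded separately. P(X ≥ 9) is the chance that a ninth failure occurs and the question arises. P(X = 9) is the chance that the wording decides whether the study is suspended at all on this criterion.

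**3. The FEV1 criteria.** Assumptions: baseline is the same-day pre-challenge FEV1, and recovery to within 85% or 90% of baseline means FEV1 of at least that percentage. FEV1 as a percentage of baseline is 100 minus the percentage fall.

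| Fall | FEV1, % of baseline | Criterion 1 | Albuterol assigned on FEV1 | At least 85% | At least 90% |
|---|---|---|---|---|---|
| 9.9% | 90.1 | pass | no | yes | yes |
| 10% | 90 | pass | yes | yes | yes |
| 12% | 88 | fail | yes | yes | no |
| 15% | 85 | fail | yes | yes | no |
| 16% | 84 | fail | yes | no | no |

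Three things follow:
- Below a 10% fall, the 85% test is met without any recovery. From 10% upward, albuterol is assigned and the untreated route is closed. That route never decides a case.
- A subject below 90% of baseline has fallen more than 10% and has already failed criterion 1. The treated route adds no failures either. This includes subjects given albuterol for symptoms alone, who are still above 90% if their fall is under 10%.
- A subject who falls 12% and recovers fails criterion 1 but satisfies the recovery test of criterion 2. Item 14 of Visit 2 sends such a subject to repeat spirometry and discharge without mentioning discontinuation or the count.

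**The case against.** The strongest reply is that staff can act on the text as it stands. The rule turns its percentage into an explicit number, that number is the stricter form, and the slip is one count wide. On the FEV1 side, criterion 2 adds a requirement and exempts nobody from criterion 1. Read literally, a fall above 10% is a failure whatever follows, so criterion 2 is redundant and does not compete over who is counted. Most of this stands, and it is why the point is minor. It does not make the two threshold sentences agree, and it does not give the untreated route any case to decide.

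A reader might also infer several stronger faults, which the documents do not support:
- *That the 6-hour limit cannot be checked, because no 6-hour spirometry is scheduled.* Six hours is a deadline. Visit 2 has a test at 4 hours and repeats spirometry before discharge after an early fall of 10% or more. Visit 0 discharge requires a reduction below 10%. The Observation Schedule holds subjects until FEV1 is back to 90% of baseline.
- *That the criteria use two different baselines, because Visit 0 lists "Baseline spirometry".* The individual criteria apply to a specific challenge, and the Observation Schedule requires spirometry before any challenge. Both point to the same-day value.
- *That it is open whether failing one criterion is enough.* The list format and the adverse event definition both point to any single failure counting.
- *That silence on safety failures at Visit 0 in subjects who then screen-fail is a contradiction.* It is missing detail only.

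**Conclusion.** The point holds as a minor defect: wrong as written, in two places.

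The percentage and the count conflict at one value, 9 of 45. The chance of finishing on exactly that value runs from 0.0003 at an assumed 5% failure rate to about 0.15 at 20%. These figures are illustrative only. They rest on a fixed base of 45, which is the base the rule itself uses.

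The untreated route in criterion 2 cannot operate alongside the albuterol clause, and the recovery tests add no failures beyond criterion 1. This rests on the same-day baseline. No frequency is claimed. The practical consequence is uncertainty about whether a subject who falls more than 10% and then recovers is meant to be discontinued and counted.

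Neither defect leaves the study without a usable suspension rule, and neither touches the primary endpoint definition or its analysis.

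**What to change.** Under Safety measures:

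1. Reconcile the percentage with the count so that both give the same answer at 9 of 45. Check the revised text at 8, 9 and 10 failures.
2. Reconcile criteria 1 and 2 with the albuterol clause, so that a reader can tell who is discontinued and who is counted, including a subject who falls more than 10% and recovers. Check the revised text at the falls tabulated above, and align item 14 of Visit 2 with it.

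The sponsor must choose the threshold and the clinical rule; neither is proposed here. The cost is protocol wording only, with no extra visits, procedures or subjects.
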